1. To test cannabis's acute effects on incentive salience of alcohol after exposure to alcohol cues and on alcohol consumption, as indexed by: 1) subjective craving for alcohol and 2) alcohol consumption (number of drinks consumed on an alcohol choice self-administration task). These domains are all components of "wanting" alcohol. We hypothesize that, relative to placebo, cannabis (with 3.1% THC, 7.2% THC) will dose-dependently increase alcohol craving and amount of alcohol consumed in the context of alternative monetary reinforcement.

2. To identify mechanisms (mediators) whereby cannabis may acutely increase alcohol motivation.

2.a. The effect of cannabis dose on increases in alcohol demand (on the alcohol purchase task) will be mediated by increases in (a) positive subjective effects, (b) aversive subjective effects (7.2% THC dose only), and decreases in executive control (c) disinhibition of prepotent response on the Stop Signal Task.

[figure not shown]
2.b. The effect of cannabis dose on increases in specific dimensions of alcohol craving (as indexed by the 3 subscales on the alcohol craving questionnaire (ACQ)) will be mediated by the following: (a) ACQ anticipation of positive benefits mediated by positive subjective effects; (b) ACQ anticipation of relief from negative affect craving subscale mediated by aversive subjective effects at the high THC dose (7.2%), (c) ACQ loss of control over drinking mediated by increases in disinhibition.

3. To identify potential moderators of cannabis's acute effect on alcohol dependent variables. The effects of cannabis dose on the dependent variables will be moderated by a) alcohol use disorder severity, b) affective vulnerability, and c) trait impulsivity such that dose-dependent effects will be greater among those with a) more severe DSM-5 alcohol use disorder, b) low tolerance for negative emotions and high sensitivity to anxiety (specific to the high THC dose), and c) greater trait impulsivity, d) greater deficits in working memory (Trail Making Test B, N-BACK, Complex Working Memory Span Tasks).

Mediators (see Figure 1)	Moderators
Positive subjective effects Aversive subjective effects Disinhibition/impulsivity (Stop Signal Task)	Alcohol use disorder (AUD) severity Affective vulnerability (distress intolerance, anxiety sensitivity) Working memory

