- 3) If a participant is unavailable to complete the study sessions in the designated timeframe, as stated in the informed consent, at the discretion of the Principal Investigator.
- 4) New report of a participant receiving treatment for alcohol or cannabis use since the study screening

Discontinuing the study

All adverse events are reported to the Brown University IRB, the study sponsor (the NIH: NIAAA), and the FDA in accordance with Investigational New Drug (IND) regulations Sec. 312.32. If either cannabis, alcohol, or their interaction are deemed to cause serious adverse events and/or life-threatening events that are determined to be study-related, we will consider discontinuation of the study on the advice of the IRB, the study sponsor, and the FDA.

12. OUTCOMES:

Primary Outcome Measure: Alcohol craving [Time Frame: prior to smoking (T_0) and at 12 minutes (T_1 : post-smoking), 47 minutes (T_2 : post neutral cues), 58 minutes (T_3 : post alcohol cues), 116 minutes (T_4 : end of Alcohol Choice block 1), and 178 minutes (T_5 : end of Alcohol Choice block 2) on the Alcohol Craving Questionnaire-Short Form-Revised (ACQ-SF-R) and a single alcohol urge item. ACQ-SF-R is assessed on a 1="strongly disagree" to 7="strongly agree" scale, with higher scores indicating greater urge, and averaged to yield a total craving score. Alcohol urge is assessed with a single item "*I have an urge for alcohol*" on a 1="strongly disagree" to 7="strongly agree scale," with higher scores indicating greater urge, at T_0 , T_1 , and T_5 .

Secondary Outcome Measure: Percent of total available alcohol consumed [Time Frame: post-smoking during the two-hour alcohol choice task during the experimental session].

13. PARTICIPANT TIMELINE: Following remote screening procedures (see data collection methods below), participants complete a baseline session followed by 3 experimental sessions. All experimental sessions are conducted at least 5 days apart and within three weeks from the previous session. If participants are unable to complete the sessions within this time frame, they may be withdrawn from the study at the discretion of the Principal Investigator. The PI allows participants to complete sessions outside of the 5-21 day timeframe due to extenuating circumstances (e.g. winter break, inclement weather, sickness, shared lab space scheduling conflicts, etc.)

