Blood Sampling Procedures. We will collect a blood sample (15.5 ml at the first draw and 16.5 ml at the subsequent four draws at each study visit) for analysis of cannabinoid plasma levels and for cannabis-induced changes in hormones and other biomarkers potentially related to appetite, inflammation and stress pre-smoking and near expected peak blood levels at termination of the smoking procedure (10 minutes post-smoking onset). Blood samples will also be obtained before cue reactivity at 37 mins post-smoking onset prior to the alcohol choice task, at the end of the first 60-min alcohol choice block (110 minutes post-smoking onset) and at the end of the second 60-min alcohol choice block (170 minutes post-smoking onset). Similar collection time points have been used successfully in prior research (Hartman et al., 2015). Blood cannabinoid levels will decline following cessation of smoking but will still be detectable and significantly different from placebo at 90 minutes post-smoking onset (Hartman et al., 2015). Collection of blood samples at pre-smoking baseline and at two time points prior to the alcohol choice task will allow for examination of the dose-dependent effects of cannabis on alcohol cue-induced craving and alcohol demand. Collection of a blood sample 60 minutes post initiation of the alcohol

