20a. STATISTICAL METHODS: The dose-dependent effect of THC on alcohol DVs: (1) post-smoking urge to drink alcohol and cue-induced alcohol craving on the ACQ, and (2) amount of alcohol consumed on the Alcohol Choice Task will be tested using repeated measures mixed model analyses. The first step in the model tests Aim 1 (the primary outcome of the grant) and includes 1) static covariates (session order number), 2) session-varying (cannabis vs placebo dose) value of the respective DV assessed before smoking or after neutral cue (craving); 3) and dummy-coded cannabis condition with placebo as the reference group. Analysis of the percent alcohol consumed will mirror the above analytic approach.

20b. Methods for Plasma THC Concentrations Analysis

All participants included in the blood data analysis had data from the pre-smoking and immediate post-smoking timepoints, with some blood draws not done for 2 to 6 participants across the other three post-smoking timepoints. Blood samples collected post-smoking in the placebo condition were assayed for the first 25 participants because THC levels remain stable in this condition over several hours. To analyze cases where the post-smoking placebo values were not available, post-smoking cannabinoid levels in the two active THC conditions were compared to the pre-smoking placebo levels, covarying for the pre-smoking value of the respective active THC dose.

Methods: Monitoring

21a. DATA MONITORING: The following data and safety monitoring plan will be implemented for the protection of research participants and data. The study coordinator will monitor protocol adherence and will report to the PI. This individual will assess adherence via direct observation of the study visits, visual inspection of the completeness of data collection, verification procedures for the scanned scantrons of the case report forms, and all participant communication outside of study visits. Weekly reporting procedures are in place for routine operations and immediate/daily communication will take place depending on the time sensitive nature of communication. The PI will be informed immediately of any adverse event.

21b. N/A

22. HARMS:

Potential Risks to Subjects.

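### Section 20a lets cue-induced craving be adjusted for a value measured after smoking, so the dose coefficient is neither the total effect in Aim 1 nor a clean cue increment

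*Combined protocol and SAP*

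**What the plan says.** Section 7 (Objectives), objective 1, concerns the incentive salience of alcohol after alcohol cues. It hypothesises that, relative to placebo, "cannabis (with 3.1% THC, 7.2% THC) will dose-dependently increase alcohol craving and amount of alcohol consumed".

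Section 20a names two craving outcomes, "post-smoking urge to drink alcohol and cue-induced alcohol craving on the ACQ". The model has session order, dummy-coded dose with placebo as reference, and as covariate the "session-varying (cannabis vs placebo dose) value of the respective DV assessed before smoking or after neutral cue (craving"). It does not say which covariate goes with which outcome. The natural reading is the pre-smoking value for post-smoking urge and the post-neutral-cue value for cue-induced craving.

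Section 12 (Outcomes) places the first assessment after smoking "at 12 minutes (T_1 : post-smoking") and the two cue assessments at "47 minutes (T_2 : post neutral cues), 58 minutes (T_3 : post alcohol cues"). Under Blood Sampling Procedures in section 18a, one sample is taken "at termination of the smoking procedure (10 minutes post-smoking onset") and another "before cue reactivity at 37 mins post-smoking onset". The same paragraph expects that cannabinoid levels "will still be detectable and significantly different from placebo at 90 minutes post-smoking onset".

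The Alcohol Cue-Reactivity paragraph of section 18a presents the neutral exposure as the control condition for the alcohol-cue response.

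**The concern.** A covariate that serves as a baseline should not be open to influence by treatment. T2 is assessed after smoking, while the drug is expected to be active. If cannabis raises craving in general, T2 rises too, and conditioning on it subtracts part of the effect from the T3 comparison.

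The protocol's own mechanisms make this plausible. Objective 2 proposes positive and aversive subjective effects and disinhibition as mediators. These are general states, and section 18a schedules their measurement after smoking and before cue exposure.

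Craving is the primary outcome. A T2-adjusted result near zero could be reported as no effect of cannabis on alcohol craving after cues, although craving after cues was in fact higher under cannabis. The word 'or' in the covariate definition also leaves open which covariate is used.

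**Working it through.** The plan gives no expected effect at T2 or T3 and no T2-T3 slope, so there is no planned figure to reproduce on this point. What follows is timing, algebra and assumed ranges.

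**1. Timing.** Smoking ends 10 min after onset. Section 12 does not state its time origin. Smoking onset fits the blood-draw times and the start of the choice task about 50 min after smoking ends.
- End of smoking to T2: 47 - 10 = 37 min.
- T1 to T2: 47 - 12 = 35 min.
- T2 to T3: 58 - 47 = 11 min.
- T2 (47 min) precedes the 90-minute mark at which drug levels are still expected to differ from placebo.

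**2. What each model estimates.** Let d2 and d3 be the cannabis-minus-placebo differences at T2 and T3, and beta the fitted slope of T3 on T2.
- Total effect on post-cue craving: d3.
- Cue increment: d3 - d2.
- T2-adjusted dose coefficient: d3 - beta*d2.

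The coefficient misses the total effect by beta*d2 and the cue increment by (1 - beta)*d2. It equals both only if d2 = 0.

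**3. Numbers (all effects assumed).**

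| Case | d2 | d3 (total) | Increment d3 - d2 | T2-adjusted, beta 0.3 | T2-adjusted, beta 0.9 |
|---|---|---|---|---|---|
| Same effect at T2 and T3 | 0.4 | 0.4 | 0 | 0.28 | 0.04 |
| Half the effect at T2 | 0.2 | 0.4 | 0.2 | 0.34 | 0.22 |
| Effect only after alcohol cues | 0 | 0.4 | 0.4 | 0.40 | 0.40 |
| Larger effect at T2 | 0.4 | 0.2 | -0.2 | 0.08 | -0.16 |

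With k = d2/d3, the share retained is 1 - beta*k. For beta from 0.3 to 0.9, the share removed is 30% to 90% at k = 1, 15% to 45% at k = 0.5, and 0% at k = 0. More than half is lost only when beta*k exceeds 0.5.

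**4. Power.** Set the T0-adjusted test to 80% power at the two-sided alpha of .017 in section 14. Assume a T0-T3 correlation of 0.3 and equal variances, so that beta equals the T2-T3 correlation r. Power with T2 adjustment is then Phi(3.229*(1 - r*k)*sqrt(1 - 0.09)/sqrt(1 - r^2) - 2.387), where 3.229 = 2.387 + 0.842.

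| r | 0.3 | 0.5 | 0.7 | 0.8 | 0.9 |
|---|---|---|---|---|---|
| k = 1 | 45% | 27% | 14% | 9% | 5% |
| k = 0.5 | 64% | 61% | 66% | 76% | 93% |
| k = 0 | 80% | 88% | 97% | about 100% | about 100% |

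Section 14 also states alpha .01. At that level the k = 1 row runs from 43% down to 3%.

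**5. Simulation check.** Three sessions, 120 participants, random intercept, total effect 0.4, alpha .017, 40 runs per cell, within-session T2-T3 correlation 0.3 to 0.85.

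| k | Share retained, T2-adjusted | Detected, T2-adjusted | Detected, T0-adjusted |
|---|---|---|---|
| 1 | 0.15 to 0.37 | 5% to 10% | 68% to 85% |
| 0.5 | 0.58 to 0.70 | 40% to 88% | 70% to 88% |
| 0 | 0.96 to 1.05 | 72% to 100% | 78% to 85% |

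The T0-adjusted share retained was 0.91 to 1.07 throughout, within the noise of 40 runs. The fitted slope was 0.52 to 0.87. It exceeds the within-session correlation because an uncentred covariate also carries between-person differences.

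**6. Not a clean cue effect either.** A second simulation used different variance components and 60 runs per scenario, with equal effects of 0.4 and no cue-specific effect. The T2-adjusted coefficient was 0.03 to 0.11, whereas T3 - T2 gave about 0.

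**The case against.** The strongest defence is that the adjustment is intended. The outcome is called cue-induced craving, the neutral exposure is there as its control, and objective 1 opens with salience after alcohol cues. On that view, removing general post-smoking craving is the purpose of the design. This stands as a reason to keep a neutral-cue comparison. It does not justify T2 as a covariate, because that model leaves (1 - beta)*d2 of the general effect in the estimate.

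Three stronger readings are tempting, and the documents do not support them.
- **That the model removes most of the cannabis effect.** This needs beta*k above 0.5, and the documents give neither quantity. If the effect appears only after alcohol cues, nothing is lost and, in the algebra of step 4, power is equal or higher.
- **That a general rise in craving would go undetected altogether.** Section 20a also tests post-smoking urge, and section 12 collects that item at T0 and T1. With a general effect of 0.4 assumed already present at T1, the T0-adjusted urge test detected it in 85% to 98% of simulated trials. That is one early time point and does not replace the post-cue result.
- **That a negative T2-adjusted coefficient would be a sign error.** With d2 = 0.4 and d3 = 0.2, the cue increment really is -0.2, so a negative sign is right for a cue estimand. It misleads only if read as the total effect.

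**Conclusion.** The point holds as a mismatch between the model and the effect it is meant to estimate, and it should be fixed. On the natural reading of section 20a, cue-induced craving is adjusted for a value taken about 37 minutes after smaking ends. The resulting coefficient is not the total increase that Aim 1 hypothesises, and it is not a clean cue increment when beta is below 1 and d2 is not zero.

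The loss of total effect ranges from none (effect only after alcohol cues) to about 90% (equal effects at T2 and T3, beta 0.9). It is 15% to 45% when the T2 effect is half the T3 effect. These figures rest on assumed values of beta and d2/d3. The post-timing facts come from the protocol; the size does not. The post-smoking urge analysis, read as adjusted for the pre-smoking value, is not affected.

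**What to change.** In section 20a:
- State the covariate for each outcome, so that 'or' no longer leaves a choice.
- Test the total effect on T3 ACQ with the same-session pre-smoking (T0) ACQ as covariate.
- For cue reactivity, replace the T2-as-covariate model with T2 and T3 as joint outcomes in a dose-by-cue model adjusted for T0, or equivalently analyse T3 - T2. Report this as a separate estimand.

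The neutral-cue comparison need not be dropped. Which of the two estimands ranks first is for the investigators to decide and state.

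**Cost.** One additional model and no new data: Table 1 already schedules the ACQ before smoking at the experimental sessions. Section 18a says the study was completed in May 2021, so this is a re-specification and reanalysis and should be reported as such. The cue contrast may be less precise. With equal variances and ignoring the T0 adjustment, its standard error relative to the T2-adjusted model is sqrt(2*(1 - r)/(1 - r^2)) = sqrt(2/(1 + r)). That is 1.24 at r = 0.3, 1.08 at r = 0.7 and 1.03 at r = 0.9.

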This human cannabis administration research will provide the most comprehensive controlled test of how cannabis affects alcohol motivation and consumption. It may yield substantial information about the mechanisms whereby cannabis may pose a risk for the development and maintenance of problem drinking; the relative roles of these different mechanisms could inform clinical treatment and prevention efforts. The outcomes of this investigation have direct implications for public health policy as they can inform efforts to reform cannabis legislation by bridging the gap between the public's considerable misconception about perceived low risks from cannabis and lesser-known risk of increased drinking from cannabis. Characterizing cannabis's putative effects on alcohol can potentially decrease consumption by framing public health messages and via regulation of advertising and retail marketing practices in states that have or will move towards cannabis legalization.

Figure 1. Mediation Model

8. TRIAL DESIGN: Repeated measures double-blind crossover design.

Methods: Participants, interventions, and outcomes

9. STUDY SETTING: Brown University, Providence, RI, United States of America.

10. ELIGIBILITY CRITERIA: English speaking, age 21 to 44, past month cannabis use \geq twice weekly and \geq weekly in the past six months, positive urine toxicology screen for THC at baseline, smoking as a familiar mode of cannabis administration, heavy episodic drinking (≥ 5 drinks for men, ≥ 4 drinks for women per occasion) \geq once monthly over the past 12 months¹, not meeting criteria for current DSM-5 major depressive episode, manic or hypomanic episode, panic disorder, or psychotic symptoms as assessed by the SCID, ability to abstain from alcohol and cannabis for 24 hours without withdrawal (Clinical Institute Withdrawal Assessment for Alcohol, revised-CIWA-AR score < 8 at each experimental visit), no intent to quit or receive treatment for cannabis or alcohol use disorder, negative pregnancy test and not nursing, negative urine toxicology screen for drugs other than cannabis, no contraindicated medical issues and body mass index ≤ 30 and weighing < 250 lbs confirmed via physical exam, no history of seizures; ≤ 20 tobacco cigarettes daily for tobacco smokers; history of simultaneous alcohol and cannabis use on the same occasion.

10a. ELIGIBILITY CRITERIA selection:

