14. SAMPLE SIZE: A sample size of 120 is required to test Primary Aim 1: cannabis's acute effects on incentive salience of alcohol after exposure to alcohol cues and on alcohol consumption, as indexed by subjective craving for alcohol and alcohol consumption (percent of total available alcohol consumed on an alcohol choice self-administration task).

Power estimates and sample size calculations were conducted with a two-tailed $\alpha = .017$ and power of at least .80 (Cohen, 1988). Effect size estimate was informed by our preliminary results and the literature (Ballard & de

Wit, 2011; Lukas & Orozco, 2001; [name] et al., 2011, 2012), which indicated a large effect of cannabis administration (3.0%THC) on positive subjective effects ($d = 2.45$), a moderate effect on negative emotional processing ($d = .56$), a small ($sr^2 = .03$) effect on disinhibition; a small effect ($d = .12$) of cannabis cue reactivity on alcohol craving. The effect size of low dose of THC combined with low dose of alcohol on self-report of “wanting more drug” was found to be large, $r^2 = .48$ (Ballard & de Wit, 2011). The effect size for a low dose of alcohol pretreatment combined with moderate dose cannabis on the number $r^2 = .47$ and duration $r^2 = .63$ of euphoric events was found to be large (Lukas & Orozco, 2001). The above referenced literature demonstrates highly relevant effect size estimates, although there is no one study that has tested directly the hypotheses in this application. Thus, we assumed conservatively that the effect of cannabis administration on alcohol craving and consumption will be at least of medium magnitude, accounting for at least 5% of the variance in a given alcohol DV. With power of .80 and alpha at .01, a sample size of 120 would be required to detect an effect of cannabis dose when tested in conjunction with the relevant covariates.

15. RECRUITMENT: Participants are recruited through advertisements in newspapers, on Craig’s list, through community bulletin boards including digital university-specific newsletters, and community-based events. Responders to study advertisements are asked to complete an initial brief screen using online survey software. If eligible, they are then screened by phone), followed by more rigorous screening at baseline for inclusion criteria.

16. Methods: Assignment of interventions (for controlled trials)

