16a. SEQUENCE GENERATION: Randomization to the cannabis dose order for the three available doses (i.e., 7.2%, 3.1%, and 0% THC) occurs before the first experimental session. The six predefined order permutations are: (1, 2, 3), (1, 3, 2), (2, 1, 3), (2, 3, 1), (3, 1, 2), and (3, 2, 1). For randomization to one of the six orders, each participant is assigned to the next available order in the sequence. Once all orders are filled, the assignment continues from the beginning of the list, ensuring all orders are used in a balanced manner.

16b. ALLOCATION CONCEALMENT MECHANISM: In order to maintain double-blind conditions (participants and research assistants), cannabis cigarettes are prepared by the PI or Co-I who randomizes participants to the cannabis dose conditions but who has no contact with study participants.

16c. IMPLEMENTATION: The PI or Co-I assigns participants sequentially to the next available drug dose order.

17a. BLINDING: Research assistants and participants remain blinded to the cannabis dose order assignment.

17b. Unblinding may be permissible if necessary in the event that an individual participant were to be discontinued from the study if their safety were at risk (e.g., adverse reaction to cannabis or alcohol for which further participation in the study is no longer safe).

18. Methods: Data collection, management, and analysis

18a. DATA COLLECTION METHODS:

The following sections describe protocol procedures from the start of study recruitment in February 2017 through March 16, 2020 when research operations were ceased due to the mandatory COVID-19 pandemic laboratory closure. The study was permitted to resume laboratory research operations in July 2020 under a modified protocol due to COVID-19 precautions and was completed in May 2021. As a result of the COVID-19 pandemic, some of the in-person research procedures were suspended. Specifically, the modified study protocol did not include blood collection or computer-based tasks during the experimental sessions. Study screening procedures were also designed to minimize in-person contact [see COVID-19 Modifications to Protocol below].

Design Overview. This project uses a within-subjects repeated measures experimental design to examine the effect of 7.2% THC and 3.1% THC dose of cannabis, relative to placebo, on alcohol craving, cue-induced incentive salience, and subsequent drinking in an alcohol choice task in which participants choose either to

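### Section 20a sets out to test dose dependence but names only dose-versus-placebo terms; it pre-specifies no 7.2% versus 3.1% THC contrast and no rule for concluding dose dependence

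*Combined protocol and SAP*

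**What the plan says.** Objective 1 (section 7) hypothesises that, "relative to placebo, cannabis (with 3.1% THC, 7.2% THC) will dose-dependently increase alcohol craving and amount of alcohol consumed". Section 20a gives the target of the analysis as "The dose-dependent effect of THC on alcohol DVs" and lists the terms of the Aim 1 model: session order, the pre-smoking or post-neutral-cue value of the outcome, and "dummy-coded cannabis condition with placebo as the reference group". For drinking it adds: "Analysis of the percent alcohol consumed will mirror the above analytic approach".

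The design (section 8) is a "Repeated measures double-blind crossover design" with three conditions. Section 16a fills six dose orders in turn, "ensuring all orders are used in a balanced manner".

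No section names a 7.2% versus 3.1% contrast, a trend test, an overall dose test, or a rule for deciding when the data show dose dependence. Section 20a lists the model terms in a complete sentence, so the gap is not explained by removed text.

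**The concern.** The claim concerns an ordering of three conditions, while the named tests concern each active dose against placebo. Both placebo comparisons can be significant when the two doses act equally, or when the lower dose acts more strongly. One can be significant and the other not by chance alone. If the report then speaks of dose dependence, the statement rests on comparing two p-values and not on a test of the difference between the doses.

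Objectives 2 and 3 build on the same idea: some pathways are predicted only at 7.2%, and moderators are predicted to strengthen dose-dependent effects. Section 7 also ties the results to public health policy.

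**Working it through.** **1. The plan's own figure.** Section 14 gives N=120 for an effect explaining 5% of variance at power .80. It does not say which test this refers to. It states "two-tailed $\alpha = .017$ and power of at least .80" and later, for the same N, an alpha of .01. I read it as a 2-df within-person test of dose with partial eta-squared .05:
- f² = .05/.95 = .0526; error df = 2(N−1) = 238; λ = f² × 238 = 12.5.
- Alpha .017: power at 120 is 79%; 80% needs N = 121–122. This reproduces 120.
- Alpha .01: power at 120 is 73%; 80% needs N = 135–136. This does not.

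So 120 fits an overall dose effect at .017. It was not derived for a difference between the active doses.

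**2. The contrast is available from the planned model.** In a balanced crossover the variance of any difference between two condition means is 2σ²/N, where σ² is the within-person residual variance. At N=120 the SE is √(2/120) = 0.129σ for 3.1% vs placebo, 7.2% vs placebo and 7.2% vs 3.1% alike. With outcome SD 1 and within-person correlation .5 (assumed; the documents give none), σ² = .5 and the SE is √(2 × .5/120) = 0.0913 SD.

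**3. What the placebo comparisons show under a plateau.** Assume the same true effect d at both doses. Then f² = d²/(3σ²); at d = 0.30, f² = .09/1.5 = .06 and partial eta-squared = .06/1.06 = 5.7%. Each placebo comparison has power of about Φ(0.30/0.0913 − 2.40) = Φ(0.88) = 81%. The two share the placebo mean, so joint results come from simulation (N=120, two-sided alpha .017):

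| Equal effect at both doses | Partial eta² | Both placebo comparisons significant | 7.2% significant, 3.1% not | Linear trend on % THC significant | 7.2% vs 3.1% wrongly significant, 7.2% higher |
|---|---|---|---|---|---|
| 0.25 SD | 4% | 48% | 16% | 58% | <1% |
| 0.30 SD | 6% | 70% | 11% | 77% | <1% |
| 0.40 SD | 10% | 96% | 2% | 96% | <1% |

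The plan's 5% lies between the first two rows. At a fixed partial eta-squared the assumed correlation drops out, since only d/σ matters.

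**4. Under a reversal.** If 3.1% is assumed 1.5 times as effective as 7.2% (about 0.45 and 0.30 SD), both placebo comparisons are significant in 82% of trials.

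**5. Power of the direct contrast.** With assumed effects of 0.13 and 0.30 SD, power is Φ(0.17/0.0913 − 2.40) = Φ(−0.54), about 30%. Scaling other assumed patterns to 5% of variance at alpha .017:

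| 3.1% effect as share of 7.2% effect | Difference (σ) | Power, N=120 | Power, N=150 | N for 80% |
|---|---|---|---|---|
| 75% | 0.110 | 6% | 7% | 1717 |
| 50% | 0.229 | 27% | 34% | 397 |
| 43% (proportional to % THC) | 0.260 | 35% | 44% | 308 |
| 25% | 0.331 | 56% | 68% | 191 |

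A linear trend test has 82% to 88% power at N=120 under these rising patterns, but also 70% under a plateau scaled to the same 5%. A significant trend therefore does not show that 7.2% exceeds 3.1%.

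**The case against.** Four points can be made for the plan.

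- **Dummy coding is only a parameterisation.** The 7.2% minus 3.1% difference is one line of output from the same fit, with the same precision. This stands. A reader might infer that the planned model cannot show a difference between the doses, and the documents do not support that.
- **The misreading is hypothetical.** Nowhere does the protocol commit to inferring dose dependence from two significant placebo comparisons. This also stands. The percentages in step 3 describe what those comparisons can and cannot tell apart; they are not error rates of a stated decision rule.
- **Alpha .017 is close to .05/3 = .0167, so three pairwise tests may have been intended.** That is possible, but section 14 does not explain the figure and then uses .01, and section 20a names no third comparison. An unstated intention is not pre-specification.
- **The hypothesis is framed relative to placebo, and a trend test is a recognised alternative.** The framing is as described, but the hypothesis also says the increase follows dose. No trend test is planned, and one alone would not separate the two active doses.

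Low power for the contrast is a further objection, and it does limit what can be required. It argues against making a significant contrast the sole permit for the term dose-dependent. It does not argue for leaving the difference unestimated.

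**Conclusion.** The point holds as a gap in pre-specification. Objective 1 and section 20a state a dose-dependence question, and the named terms answer a different one: whether each dose differs from placebo. The contrast, the alpha and the basis for a dose-dependence statement are missing for both craving and percent alcohol consumed. The placebo comparisons themselves are unaffected.

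Near the plan's 5% effect size, a plateau would make both placebo comparisons significant in roughly half to 70% of trials, so that result says little about the shape of the response. These figures rest on assumed effects, correlation .5, N=120 and alpha .017. The power figures for the contrast also depend on assumed dose patterns, because the documents give no expected difference between 7.2% and 3.1%. The change is worth making and does not call the design into question.

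**What to change.** Keep the dummy coding and add to section 20a, for craving and for percent alcohol consumed:

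1. The 7.2% versus 3.1% contrast from the same fitted model, reported with its estimate and confidence interval.
2. An order of testing: the 2-df dose effect first, then, if significant, the three pairwise contrasts at the same alpha. With three conditions this is a closed procedure and needs no further correction within an outcome.
3. One stated alpha, after reconciling the .017 and .01 in section 14.
4. A rule that any statement of an increase from 3.1% to 7.2% rests on this contrast, not on comparing the two placebo p-values or on a trend test alone. If the contrast is inconclusive, report cannabis-versus-placebo effects and do not claim a plateau.

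Section 18a says the study was completed in May 2021, so the contrast should be labelled as added afterwards.

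The cost is one contrast statement per model and no new data. The drawback is that dose dependence becomes harder to claim: power is about 30% at 0.13 and 0.30 SD, and 6% to 56% across the other patterns at N=120. The confidence interval will often be the main result.
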